## LIST OF ABBREVIATIONS

Abbreviation or special term	Explanation
AE	adverse event
AESI	adverse event of special interest
ATC	Anatomical Therapeutic Chemical (Classification System)
AZ	AstraZeneca
BID	twice a day ( bis in die )
BMI	body mass index
BP	blood pressure
bpm	beats per minutes
CAT	COPD assessment test
CEC	Clinical Events Committee
CI	confidence interval
COPD	chronic obstructive pulmonary disease
CR	copy reference
CSP	clinical study protocol
CSR	clinical study report
CV	cardiovascular
DB	database
DSMB	Data Safety Monitoring Board
DPI	dry powder inhaler/inhalation
ECG	electrocardiogram, electrocardiographic
eCRF	electronic case report form
EDC	electronic data capture
eGFR	estimated glomerular filtration rate
EOS	end of study
EOT	end of treatment
FAS	full analysis set
FEV 1	forced expiratory volume after one second
FVC	forced vital capacity
GOLD	Global Initiative for Chronic Obstructive Lung Disease
HLT	high level term
ICF	informed consent form
ICS	inhaled corticosteroid
IP	investigational product
IWRS	interactive web response system
J2R	jump to reference
KM	Kaplan-Meier

Abbreviation or special term	Explanation
LABA	long-acting $\beta_2$ -adrenergic agonists
LAMA	long-acting muscarinic antagonist
LTFU	lost to follow-up
MACE	major adverse cardiovascular event(s)
MAR	missing at random
MedDRA	Medical Dictionary for Regulatory Activities
MI	myocardial infarction
MMRM	mixed model for repeated measures
NI	non-inferior, non-inferiority
OS	overall survival
PCS	potentially clinically significant
PDE4	oral phosphodiesterase type 4
PID	patient identification number
PT	preferred term
PTFU	post treatment follow-up
QTc	QT Interval corrected for heart rate
QTcB	QT Interval corrected for heart rate using the Bazett formula ( $QTcB = QT/(RR)^{1/2}$ )
QTcF	QT Interval corrected for heart rate using the Fredericia formula ( $QTcF = QT/(RR)^{1/3}$ )
SABA	short-acting $\beta_2$ -adrenergic agonists
SAE	serious adverse event
SAMA	short-acting muscarinic antagonist
SAP	statistical analysis plan
SD	standard deviation
SMQ	standard MedDRA query
SOC	system organ class
Sponsor	AstraZeneca
TEAE	treatment-emergent adverse event
WHO DD	World Health Organization Drug Dictionary

## AMENDMENT HISTORY

---

Date	Brief description of change
30 Oct 2013	Initial Approved SAP by Forest Lab
26 May 2016	Amend according to Amended Protocol #2 (15 Sep 2015), Amended Protocol #3 (29 Feb 2016) and AstraZeneca (AZ) standard
17 August 2017	Amend according to FDA comments on the SAP amendment 1 (dated May 26, 2016), JAC recommendations, and/or blind delivery reviews.
23 October 2017	Amend according to blind delivery reviews, particularly adding 2 subgroup analyses for LABA users and LABA/ICS users.

---

## 1. STUDY DETAILS

### 1.1 Study objectives

Objectives:	Outcome Measure* :

To assess the safety of acclidinium bromide on major adverse cardiovascular events (MACE)
	
Primary Outcome Measure:
 
 
• Time to first MACE, where MACE for the analyses is defined as any adjudicated event which is a composite of the total of cardiovascular (CV) death, non-fatal myocardial infarction (MI), or non-fatal stroke
 
 
Secondary Outcome Measure:
 
 
• Time to first MACE or other serious CV events of interest (e.g., adjudicated serious adverse events [SAEs] based on standard MedDRA query [SMQ] of cardiac disorders [i.e. cardiac arrhythmias SMQ and cardiac failure SMQ] and of cerebrovascular disorders
 

To assess the overall safety of acclidinium bromide
	
Safety Outcome Measures:
 
 
• Adverse events (AEs, includes SAEs) including chronic obstructive pulmonary disease (COPD) exacerbations
 
• Vital sign measurements
 
• Electrocardiograms (ECG) parameters
 
• Physical examination findings
 

To assess whether acclidinium bromide reduces moderate or severe COPD exacerbations
	
Primary Outcome Measure:
 
 
• Rate of moderate or severe COPD exacerbations per patient per year during the first year of treatment               
 
○ Primary analysis: on-treatment analysis
 
○ Secondary analysis: on-study analysis
 
 
 
 
Secondary Outcome Measure:
 
 
• Rate of hospitalizations due to COPD exacerbations per patient per year during the first year of treatment
 

\* Only primary and secondary efficacy outcome measures and safety outcome measures are listed. The additional efficacy outcome measures and CAT assessment are described in Section 3.

## 1.2 Study design

This is a Phase IV, multicenter, randomized, double-blind, placebo-controlled, parallel-group study evaluating the effect of Acclidinium Bromide (a long-acting muscarinic antagonist delivered by the Pressair® dry powder inhalation [DPI] device) compared with placebo on long-term CV safety and COPD exacerbations in outpatients at least 40 years of age who have been diagnosed with moderate to very severe COPD (postbronchodilator % predicted forced expiratory volume in 1 second [FEV1] < 80% and FEV1/forced vital capacity [FVC] ratio < 70%) and a history of CV or cerebrovascular disease and/or significant CV risk factors.

Note: in this document

1. The term “double-blind treatment period” applies to the following 2 scenarios:
  - When used in “maximum of 36-months double-blind treatment period”
  - When used for patients who completed 36-months treatment (completer)
2. The term “during the treatment period” refers to on-treatment period.
3. The term “during the whole study period” refers to both on-treatment and off-treatment (post-treatment follow-up) periods.

The study consists of two-week washout/run-in period (for patients on a long-acting muscarinic antagonist [LAMA]) followed by a maximum of 36-month double-blind treatment period.

Signed informed consent form (ICF) from the patient or the patient’s legally authorized representative will be obtained before any study-related procedures are begun. All patients will be assigned a patient identification (PID) number via the interactive web response system (IWRS). Patients meeting the entry criteria for this study will be randomized (1:1) to acclidinium bromide 400 µg (abbreviated as acclidinium hereafter) twice a day (BID) or placebo BID. This study will conclude when 122 patients have experienced an adjudicated MACE.

Patients who prematurely discontinue investigational product (IP) will participate in a post-treatment follow-up period. The follow-up period will include on-site visits and telephone visits to collect MACE, COPD exacerbations, concomitant medications, and SAEs for the remainder of the study duration.

An independent Data Safety Monitoring Board (DSMB) will be established for this study. The DSMB will periodically monitor and review relevant clinical safety data, including adjudicated MACE.

Patients will be assessed according to the Schedule of Evaluations (See Section 2 of the clinical study protocol [CSP]).

## **1.3 Number of subjects**

### **1.3.1 Power for the primary safety endpoint: time to first MACE event**

For this study, a total of 122 patients with MACE will be needed to have 90% power, at 5% significance level, to rule out a hazard ratio of 1.8 in time to first MACE in acclidinium bromide treated patients relative to placebo, assuming the hazard rate is 1.0 under the alternative hypothesis. The justification for the hazard ratio of margin of 1.8 is provided in Appendix IV of the CSP.

This ASCENT COPD study will be recruiting patients with a FEV1 below 80% and a planned maximum of 36 months double-blind treatment period. The assumption of 1.9 MACE per 100 patient years would be reasonable for this study (See Section 9.7.9.1 of the CSP for details). To obtain 122 MACE in this study with 1.9 MACE per 100 patient years of treatment, a total of 6,500 patient years of treatment (aclidinium bromide and placebo) would be needed. Assuming a treatment discontinuation rate of 40% and a study discontinuation rate of 20% at year 2, and following an exponential distributions for time to events and time to discontinuations, a sample size of 4000 is needed to ensure 90% power to observe 122 events applying the on-study analysis, and an 80% power to observe 91 events applying the on-treatment analysis.

### **1.3.2 Power for the primary efficacy endpoint: rate of moderate or severe exacerbations per patient per year during the first year of treatment**

The sample size of 4,000 patients after 1 year of treatment will have ~89% power to detect a reduction in the rate of moderate or severe COPD exacerbations per patient per year during the first year of treatment of 14% (rate ratio of 0.86 in acclidinium bromide relative to placebo) at 0.05 significance level. The 89% power was calculated assuming a treatment discontinuation rate of 30% during the first year, a placebo rate of 0.8 exacerbation per patient per year (reduced from 1 to 0.8 as not all patients will have a history of exacerbation prior to randomization), and an overdispersion factor  $k$  of 0.67 (Keene et al, 2007).

See Section 9.7.9 of the CSP for detailed information on determination of sample size and power calculation.

## **2. ANALYSIS SETS**

### **2.1 Definition of analysis sets**

Three populations will be considered in the statistical analysis of the study.

#### **2.1.1 Screened Population**

The Screened Population will consist of all patients who signed a written ICF and received a screening number.

### **2.1.2 Randomized Population**

The Randomized Population will consist of all patients in the Screened Population who were randomized to a treatment group in the study.

### **2.1.3 Full Analysis Set Population**

The Full Analysis Set (FAS) Population will consist of all patients in the Randomized Population who took at least one dose of the double-blind IP (acridinium bromide or placebo). Patients will be analyzed according to their randomized treatment.

The FAS will be used to carry out the primary analysis of both efficacy and safety data. Efficacy and safety data may be further investigated and sensitivity analyses may be performed using the Randomized Population if more than 1% of patients did not receive one dose of the double-blind IP. Any important deviations from the randomized treatment assignment and any subjects who have received double-blind IP without being randomized will be listed and considered when interpreting the data.

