## **2.2 Violations and deviations**

### **2.2.1 Protocol deviations**

Only important protocol deviations (in the CSP referred to as protocol violations) will be listed and tabulated in the clinical study report (CSR). Protocol deviations that may greatly impact the completeness, accuracy, and/or reliability of the study data or that may significantly affect a subject's rights, safety, or well-being, will be considered as important and will include the following:

- Key eligibility criteria not fulfilled but randomized
- Concomitant use of disallowed medications. Patients who use one or more disallowed medication (for any reason, unless otherwise specified) on IP during the treatment period will be classified as protocol deviators after confirmation by an AZ physician
- Patients who received the incorrect study treatment or study dose at any time during the treatment period
- Patients who fulfilled withdrawal criteria during the study but were not withdrawn

The final list of protocol deviations will be finalized and documented prior to unblinding the study data.

All important protocol deviations will be programmatically derived. The programming produces a draft list of important protocol deviations for the medical/clinician review on an ongoing basis; a final list of important protocol deviations is determined before the database (DB) lock after a joint team review (the third bullet above is determined after the DB lock and unblinding) and include into the relevant dataset.

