## **3.5.2 Adverse events**

Adverse events will be coded using the MedDRA version 18.0 or newer.

Adverse event data will be categorized according to their onset date, as occurring during washout/run-in, during on treatment, or during off treatment.

An AE will be considered a treatment-emergent adverse event (TEAE) if it started on or after the date of the first dose of double-blind IP or it started before the date of the first dose of double-blind IP and continued during the study with increased severity. An AE that occurs more than 15 days after the date of the last dose of double-blind IP will not be counted as a TEAE.

A TEAE with cause Reasonable Possibility related to the double-blind IP as judged by the investigator is defined as a treatment related AE.

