#### **4.2.5 Safety analyses**

All safety analyses will be based on the FAS Population. No multiplicity adjustment will be made to CIs. All p-values will be unadjusted. The analyses of the secondary safety endpoint of the time to first MACE or other serious CV events of interest will not be adjusted for multiple comparisons.

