#### Sensitivity analysis

To account for the relation of the occurrence of an event and treatment exposure, an on-treatment analysis will be conducted and this will include only events that occurred while the patient was exposed to study treatment, i.e., events that occurred after the patient's last

treatment dose will be censored. Two ascertainment windows, 0 and 15 days, will be evaluated in the on-treatment analyses. The on-treatment and on-treatment +15 days analyses will censor events that occur after and more than 15 days after, respectively, after the last treatment dose (see Section 9.7.6.1 of the CSP for consideration on totality of evidence from on-study and on-treatment analyses in evaluation of MACE).

To assess possible effects of informative censoring, sensitivity analysis (on-study analysis) will be done as follows: based on the missing follow-up time in drop-outs, i.e. the time from censoring to study closure, the expected number of events that might have been observed if the drop-outs had completed the study can be calculated using an event rate similar to that observed in the study. The test (aclidinium versus placebo) will be recalculated with these residual events allocated in different proportions to the treatment groups to assess the robustness of the results with regard to the censoring of drop-outs.

Sensitivity analysis of the primary composite endpoint will also include analysis with CV death replaced with all-cause mortality.

**Subgroup analysis.** To evaluate the consistency in the primary safety endpoint over selected baseline characteristics, subgroup analysis will be performed. The subgroup is described below:

- History of at least one exacerbation in the past year ( $0, \geq 1$ )

The subgroup analysis on time to first adjudicated MACE will be analyzed using the same method as the primary analysis on the primary safety endpoint using a 95% CI and without statistical testing for NI (NI margin will not be used).

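### TEAE, on-treatment SAE and AESI summaries are tied to the randomized arm, so events in a patient given the other product are counted under a product that patient may not have taken

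*SAP*

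**What the plan says.** - **Populations.** SAP 2.1: "Three populations will be considered in the statistical analysis of the study". They are Screened, Randomized and FAS. None is defined by treatment received.
- **Attribution.** SAP 2.1.3: "The FAS will be used to carry out the primary analysis of both efficacy and safety data", and "Patients will be analyzed according to their randomized treatment". The optional extra set for sensitivity analyses is the Randomized Population, which does not follow product received either.
- **Safety.** SAP 4.2.5: "All safety analyses will be based on the FAS Population".
- **Exposure-based outputs.** SAP 3.5.2 counts an AE as treatment-emergent "if it started on or after the date of the first dose of double-blind IP" (or if it began earlier and worsened), up to 15 days after the last dose. SAP 4.2.5.3 uses the same 15-day limit for on-treatment SAEs. Of the on-treatment MACE sensitivity analysis, SAP 4.2.5.1 says "this will include only events that occurred while the patient was exposed to study treatment".
- **Wrong treatment.** SAP 2.2.1 names as an important deviation "Patients who received the incorrect study treatment or study dose at any time during the treatment period". These cases are determined after database lock and unblinding, and important deviations are listed and tabulated in the CSR. SAP 2.1.3 adds that important departures from the assigned treatment, and subjects dosed without being randomized, "will be listed and considered when interpreting the data".

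**The concern.** The exposure-based summaries use dose dates to decide whether an event counts, but they ignore which product was inhaled on those dates. If a patient randomized to placebo is given aclidinium, a TEAE on aclidinium is tabulated under placebo, and the reverse also holds. Listing the patient does not move the event.

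The stake is the AE comparison. Mixing products across columns makes the arms look more alike, and in a safety study that is the reassuring direction. The on-treatment MACE analyses share the weakness in a lesser role, since they are meant to relate events to exposure.

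Timing also matters. Wrong-treatment cases become known only after unblinding, so any rule for handling them that is written at that point would be post hoc.

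**Working it through.** **1. Does any later section override 2.1.3?** Reading 2.1.3 and 4.2.5 together binds all safety outputs to the randomized arm. The TEAE definition (3.5.2), the MACE sensitivity analyses (4.2.5.1), the AE, SAE and AESI summaries (4.2.5.3) and the list of changes from protocol (Section 5) contain no exception. The nearest thing is the duplicate-patient rule in 4.1. It keeps all of a duplicate patient's AE data if the treatment was the same at every entry, and only the first entry if treatments differed. The plan therefore takes account of product for AEs there, but has no matching rule for a wrong kit.

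**2. The plan's own event counts.** Inputs from SAP 1.3.1: margin 1.8, true hazard ratio 1.0, 5% significance (taken as two-sided), 1:1 allocation.

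Events = 4(z₀.₉₇₅ + z_power)² / (ln 1.8)², with (ln 1.8)² = 0.3455.
- 90% power: 4(1.960 + 1.282)² / 0.3455 = 121.6, so 122.
- 80% power: 4(1.960 + 0.842)² / 0.3455 = 90.9, so 91.

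Both agree with the SAP. The present point does not depend on them.

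**3. Size of the dilution.** The SAP gives no mis-dispensing rate, so p is an assumption. Suppose a share p of each arm takes the other product for the whole study, events are infrequent, and these patients otherwise resemble the rest.
- Hazard ratio seen by randomized arm, true value 1.8: [1.8(1 − p) + p] / [(1 − p) + 1.8p].
- AE risk difference seen by randomized arm: with true risks a and b, [(1 − p)a + pb] − [(1 − p)b + pa] = (1 − 2p)(a − b).

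| p | patients of 4,000 | hazard ratio seen | share of AE difference kept |
|---|---|---|---|
| 0.1% | 4 | 1.798 | 99.8% |
| 1% | 40 | 1.778 | 98% |
| 2% | 80 | 1.756 | 96% |
| 5% | 200 | 1.692 | 90% |

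For example, at 5%: (1.71 + 0.05) / (0.95 + 0.09) = 1.76 / 1.04 = 1.692.

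**4. A milder case.** If 1% of patients had one wrong month out of 36, the effective p is 0.01 / 36 = 0.00028 and the same formula gives 1.799.

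**5. Side calculation.** Suppose the 1.8 criterion were applied to an on-treatment analysis with 91 events. The standard error of the log hazard ratio is 2/√91 = 0.210. The chance of passing when the true value is 1.8 is Φ[(ln 1.8 − ln HR seen)/0.210 − 1.96]: 0.025 at p = 0, 0.029 at 1%, 0.033 at 2% and 0.048 at 5%.

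**The case against.** The strongest reply is that no formal decision rests on the affected outputs. SAP 4.2.5.1 attaches the 1.8 rule to the on-study Cox analysis, where attribution by randomized arm is right. The on-treatment analyses are sensitivity analyses and the AE tables are descriptive. A reader might infer from step 5 that the non-inferiority test has an inflated error rate. The SAP does not support that, because it sets no 1.8 criterion for the on-treatment analysis. What remains is that 4.2.5.1 refers to CSP 9.7.6.1 on weighing on-study and on-treatment evidence together, so the on-treatment result has some weight in interpretation.

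A reader might also infer that safety data in general are misattributed, or that wrong-treatment cases are ignored. Neither follows. The problem arises only for patients who actually received the wrong product, whose number is unknown and may be zero. The plan commits to listing and tabulating them and considering them in interpretation. With by-patient AE listings as well, a careful reader could trace the cases. That is real mitigation, but it changes no count and does not say how the cases would alter a conclusion.

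The scenarios in step 3 are severe: the deviation in 2.2.1 covers wrong treatment at any time, which includes a single wrong kit, and nothing in the SAP suggests 200 patients on the wrong product throughout. This objection stands and limits the size of the point.

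Reassignment also has a cost. A MACE comparison by treatment received is no longer strictly randomized, and patients dosed without randomization have no randomized comparator. That argues for making the MACE repeat supplementary and for keeping those patients out of the arm columns.

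**Conclusion.** The point holds for TEAE, on-treatment SAE and AESI summaries. The SAP defines them by exposure, foresees wrong-product receipt, and still counts the events under the randomized arm. The direction is toward no difference, provided that mis-dispensed patients carry the same risk as others on the product they took.

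The size cannot be fixed from the SAP. It is negligible if cases are few or brief. It becomes noticeable only with something like a systematic kit error, where 5% of each arm on the other product throughout would lose a tenth of an AE difference.

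The primary on-study MACE test and the efficacy analyses are not affected by this criticism. The correction is worth making because it is cheap now and would be post hoc once the cases are known.

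**What to change.** - In SAP 2.1.3 and 4.2.5, state that TEAE, on-treatment SAE and AESI summaries use treatment actually received.
- Fix one assignment rule before unblinding for patients who received both products. The product taken for the longer time, or counting any aclidinium exposure as aclidinium, would each be workable.
- Keep on-study MACE and all efficacy analyses by randomized arm.
- If any patient received the wrong product, repeat the on-treatment and +15-day MACE sensitivity analyses by treatment received, labelled as supplementary. The versions by randomized arm stay.
- Keep patients dosed without randomization out of the arm comparison and show their AEs separately.

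**Cost.** A few sentences of SAP text and one treatment-received variable, built on cases that 2.2.1 already requires to be derived. Denominators of these tables may differ from the FAS arms by a few patients, which needs a footnote. The supplementary MACE comparison gives up strict randomization and should be described that way.

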## **2.2 Violations and deviations**

### **2.2.1 Protocol deviations**

Only important protocol deviations (in the CSP referred to as protocol violations) will be listed and tabulated in the clinical study report (CSR). Protocol deviations that may greatly impact the completeness, accuracy, and/or reliability of the study data or that may significantly affect a subject's rights, safety, or well-being, will be considered as important and will include the following:

- Key eligibility criteria not fulfilled but randomized
- Concomitant use of disallowed medications. Patients who use one or more disallowed medication (for any reason, unless otherwise specified) on IP during the treatment period will be classified as protocol deviators after confirmation by an AZ physician
- Patients who received the incorrect study treatment or study dose at any time during the treatment period
- Patients who fulfilled withdrawal criteria during the study but were not withdrawn

The final list of protocol deviations will be finalized and documented prior to unblinding the study data.

All important protocol deviations will be programmatically derived. The programming produces a draft list of important protocol deviations for the medical/clinician review on an ongoing basis; a final list of important protocol deviations is determined before the database (DB) lock after a joint team review (the third bullet above is determined after the DB lock and unblinding) and include into the relevant dataset.

